Screening for eligibility for Study RHY should occur during the last visit (Week 52) of the originating study. However, in particular circumstances, entry into Study RHY may occur after Week 52 of the originating study after consultation with the sponsor (see Section 6.1). More details on treatment groups and administration of the investigational product are described in Section 7.1.

Extension Period, Including Blinded, Randomized Withdrawal–Retreatment (Period 2):

Eligibility criteria for participation in randomized withdrawal are defined as one of the following:

- ASDAS <1.3 at Weeks 16 and 20,
OR
- ASDAS <1.3 at Week 16 and ASDAS <2.1 at Week 20,
OR
- ASDAS <2.1 at Week 16 and ASDAS <1.3 at Week 20.

Patients who DO NOT meet entry criteria for participation in the 40-week double-blind, placebo-controlled, randomized withdrawal–retreatment period (i.e., patients who have not achieved a state of sustained remission) will continue to receive uninterrupted ixekizumab therapy and are referred to as Group A.

Patients who DO meet entry criteria for participation in the 40-week double-blind, placebo-controlled, randomized withdrawal–retreatment period (i.e., patients having achieved a state of sustained remission) are referred to as Group B and will be re-randomized at Week 24 as follows:

- Patients in the ixekizumab 80 mg Q2W treatment group will be re-randomized 2:1 at Week 24 to either ixekizumab 80 mg Q2W or placebo. Patients who experience a flare will return to treatment with ixekizumab 80 mg Q2W.
- Patients in the ixekizumab 80 mg Q4W treatment group will be re-randomized 2:1 at Week 24 to either ixekizumab 80 mg Q4W or placebo. Patients who experience a flare will return to treatment with ixekizumab 80 mg Q4W.

A flare is defined as follows:

- ASDAS ≥ 2.1 at 2 consecutive visits, or ASDAS > 3.5 at any visit during Period 2 and/or Period 3.

Long-Term Extension Period (Period 3):

Group A: All patients will continue to receive uninterrupted ixekizumab therapy. During Period 3, patients in Group A receiving ixekizumab 80 mg Q4W may have their dose escalated to ixekizumab 80 mg Q2W if the investigator determines that the patient may benefit from an increase in frequency of dosing to achieve adequate disease control.

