7.4. Dosage Modification

As described in Section 5.1, if a patient who has achieved a state of sustained remission (Group B) during the randomized withdrawal-retreatment period experiences a flare and meets the criteria for retreatment, the patient will be retreated with the ixekizumab treatment regimen that he or she was receiving prior to withdrawal (ixekizumab 80 mg Q2W or ixekizumab 80 mg Q4W). During Period 2, retreatment will begin at the next scheduled visit. During Period 3, given the longer interval between visits, retreatment may begin at the next scheduled visit or at an unscheduled visit prior to the next scheduled visit.

As of Week 64, patients in Group A receiving ixekizumab 80 mg Q4W may have their dose escalated to ixekizumab 80 mg Q2W in Period 3 if the investigator determines that the patient may benefit from an increase in frequency of dosing to achieve adequate disease control. Dose escalation may begin at the next scheduled visit or at an unscheduled visit prior to the next scheduled visit.

As of Week 64, patients in Group B ([Table RHBY.3](#)):

- who are receiving placebo will remain on placebo, and will be monitored per the Schedule of Activities (Section 2) for eligibility (i.e., flare) to be retreated with the ixekizumab treatment regimen they were receiving prior to withdrawal (ixekizumab 80 mg Q2W or ixekizumab 80 mg Q4W).
- who are receiving ixekizumab 80 mg Q4W may have their dose escalated to ixekizumab 80 mg Q2W in Period 3 if the investigator determines that the patient may benefit from an increase in dosing to achieve adequate disease control. Escalation to ixekizumab 80 mg Q2W may occur only after the patient has been retreated upon flare with the ixekizumab treatment regimen received during Period 1 (ixekizumab 80 mg Q4W) for at least 12 weeks.
- who are receiving ixekizumab 80 mg Q2W will remain on this dose until completion of the study or early discontinuation.

Table RHY.3. Dosage Modification for Group B during Period 2 and Period 3

Period 1 (Open-Label)	Period 2 (Blinded)	Period 3 (Blinded)	If Flare during Period 2 or 3, Retreat (Open-Label)	12 Weeks after Retreat, Escalate (Period 3) (Open-Label)
ixekizumab 80 mg Q2W	ixekizumab 80 mg Q2W	ixekizumab 80 mg Q2W	ixekizumab 80 mg Q2W	N/A
	placebo	placebo	ixekizumab 80 mg Q2W	N/A
ixekizumab 80 mg Q4W	ixekizumab 80 mg Q4W	ixekizumab 80 mg Q4W	ixekizumab 80 mg Q4W	ixekizumab 80 mg Q2W
	placebo	placebo	ixekizumab 80 mg Q4W	ixekizumab 80 mg Q2W

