10.2. Populations for Analyses

For purposes of analysis, the following major patient populations are defined ([Table RHBY.5](#)).

Table RHBY.5. Major Patient Populations for Study RHBY

Population	Description
Lead-In Period Safety Population	All patients who receive at least 1 dose of ixekizumab in Period 1.
Randomized Withdrawal Intent-to-Treat (ITT) Population	All patients who are randomized in Period 2 (Group B), even if the patient does not receive the correct treatment or does not follow the protocol. Patients will be analyzed according to the treatment which they were assigned.
Randomized Withdrawal Safety Population	All patients in Group B who receive at least 1 dose of study treatment after Period 2 randomization. Patients will be analyzed according to the treatment to which they were assigned.
Ixekizumab Structure Population	All patients who (i) are from either RHBV or RHBW study; (ii) have been treated with ixekizumab for at least 18 months; and (iii) have mSASSS data at both Week 0 in the originating study and Week 56 in RHBY.
Long-Term Ixekizumab Treatment Efficacy Population	All patients who are randomized to ixekizumab 80 mg Q2W or ixekizumab 80 mg Q4W at Week 0 of the originating studies and consistently received ixekizumab in RHBY.
Flare Population	All patients in Group B who experience a flare after randomization at Week 24 and who receive ixekizumab retreatment after flare in Period 2 and Periods 2 and 3 combined (exploratory analyses).
Follow-Up Period Population	All patients who receive at least 1 dose of study treatment at any time during Study RHBY and enter the Post-Treatment Follow-Up Period (Period 4). Patients will be analyzed according to the treatment they were taking before entering Period 4.

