### **6.1.1. Analysis Populations**

The following analysis populations will be used to address the study objectives.

**Lead-In Period Safety Population:** Unless otherwise specified, safety summaries for Combined Periods 1, 2, and 3 will be conducted on the Lead-In Period Safety Population, defined as all patients who receive at least 1 dose of ixekizumab in Period 1 in RHBY. Patients who do not meet entry criteria for participation in the randomized withdrawal-retreatment period (Group A) will continue to receive ixekizumab 80 mg Q2W or ixekizumab 80 mg Q4W. Patients who meet the entry criteria (Group B) may be randomized to ixekizumab or placebo at Week 24. Patients randomized to placebo may be retreated upon flare with the ixekizumab regimen that they received in Period 1. The data while on placebo is not included in the combined period analysis. For immunogenicity data analysis during the combined periods 1, 2, and 3, all data will be included regardless of being re-randomized to placebo or ixekizumab. Patients will be analyzed according to the treatment they were receiving at the start of Period 1.

**Long-Term Ixekizumab Treatment Efficacy Population:** Unless otherwise specified, efficacy and health outcome for Combined Periods 1, 2, and 3 will be summarized for the Long-Term Ixekizumab Treatment Efficacy Population, defined as patients who are randomized to ixekizumab 80 mg Q2W or ixekizumab 80 mg Q4W at Week 0 of the originating studies and consistently receive the same treatment regimen through Week 64 in RHBY. Patients who were randomized to placebo or adalimumab in any of the originating studies, patients who switched from IXEQ4W to open label to IXEQ2W during the originating study of RHBY, patients who were randomized to placebo during Period 2 of RHBY, and patients who were retreated during Period 2 of RHBY are not included in this population. Patients will be analyzed according to the ixekizumab regimen they were randomized to at Week 0 of the originating study.

**Ixekizumab Structure Population:** The analysis of 2-year radiographic progression in spine, measured by the change in mSASSS in patients with active rad-axSpA, will be conducted on Ixekizumab Structure Population, defined as all patients who i) are from either RHBV or RHBW study; and ii) have mSASSS data at both Week 0 in the originating study and Week 56 in RHBY.

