#### **6.1.2.2. Long-Term Ixekizumab Treatment Efficacy Population**

Efficacy and health outcome data will be summarized for the Long-Term Ixekizumab Treatment Efficacy Population (see definition in Section 6.1.1) from Week 0 in the originating study to the visit at Week 64 and Week 104, respectively, in RHYB. For patients who were escalated from ixekizumab 80 mg Q4W to ixekizumab 80 mg Q2W after Week 64, only data while on ixekizumab 80 mg Q4W will be included. If the patient early terminates the originally assigned treatment (including retreatment and escalation) prior to Week 104, then the modified nonresponder imputation (mNRI) method will be applied for categorical endpoints, and modified baseline observation carried forward (mBOCF) will be applied for continuous endpoints from the early termination visit through Week 104.

The long-term treatment effect on a categorical variable is measured by the proportion of patients who have achieved or maintained a response (see algorithm in [Table RHY.6.4](#)) through Week 64 and Week 104, respectively, and the long-term treatment effect on a continuous variable is measured by change (or percent improvement) from baseline in the originating study.

The long-term treatment effect in categorical variables using observed cases, and continuous variables using observed cases and mBOCF will be summarized (as described in Section [6.1](#)) by treatment group (see [Table RHY.6.1](#)) at each scheduled visit from Week 0 in originating study. An alternative method to handle the missing data after Week 64 for the period of Week 0 in the originating study to Week 104 in RHY, mNRI method will be applied for categorical variables and mixed model for repeated measures (MMRM) will be applied for continuous variables. Data will also be summarized graphically using the response rate for categorical variables and mean for continuous variables by group at each scheduled visit. The time points during the Extension Period (Period 2) will follow the scheduled visits for group A patients with between-visits-interval of 8 weeks.

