When the MMRM is used, the model will include treatment, originating study, geographic region, baseline value, visit, baseline value-by-visit, and treatment-by-visit interaction as fixed factors. The covariance structure to model the within-patient errors will be unstructured. The restricted maximum likelihood (REML) will be used. The Kenward-Roger method will be used to estimate the denominator degrees of freedom. The least-squares (LS) means will be reported to assess the maintenance of treatment effect; the 95% CI will also be reported. If the unstructured covariance matrix results in a lack of convergence, the heterogeneous Toeplitz covariance structure, followed by the heterogeneous autoregressive covariance structure, followed by the compound symmetry will be used. This order is specified according to a decreasing number of covariance parameters in the structure. The sandwich estimator (Diggle et al. 1994) for the covariance estimation will be used by specifying the EMPIRICAL option in SAS PROC MIXED. When sandwich estimation is used, the Kenward-Roger approximation for denominator degrees of freedom cannot be used. Instead, DDFM= BETWITHIN option will be used to estimate denominator degrees of freedom.

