#### **6.1.5. General Considerations for Analyses during the Long-Term Extension Period (Period 3)**

Unless otherwise specified, Period 3 starts at the first injection of study treatment at Week 64 or next injection date after Week 64 if injection date of Week 64 is missing and ends on the date of Week 104 or the ETV before the date of Week 104.

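### SAP 6.1.1 drops ixekizumab-arm patients retreated in Period 2 from the long-term efficacy population, which raises the mNRI long-term response rates by about one point

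*SAP*

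**What the plan says.** Protocol Table RHBY.5 (Section 10.2) defines this population as patients randomised to ixekizumab "at Week 0 of the originating studies and consistently received ixekizumab in RHBY". It does not mention flare or retreatment.

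For the Q4W arm, Protocol 5.1 says "Patients who experience a flare will return to treatment with ixekizumab 80 mg Q4W"; the Q2W arm has the matching sentence. Retreatment of an ixekizumab-arm patient is therefore the same drug on the same regimen.

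SAP 6.1.1 narrows the population to patients on one unchanged regimen up to Week 64. It then lists exclusions, among them patients re-randomised to placebo and, separately, the retreated: "patients who were retreated during Period 2 of RHBY are not included in this population".

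SAP 6.1.2.2 gives an imputation rule for the same population: "If the patient early terminates the originally assigned treatment (including retreatment and escalation) prior to Week 104", mNRI is applied to categorical endpoints and mBOCF to continuous ones. SAP 6.3.2 makes retreatment due to a flare a nonresponse under mNRI. A later sentence in 6.1.2.2 introduces mNRI and MMRM differently: "An alternative method to handle the missing data after Week 64".

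**The concern.** Membership of the population depends on what happened after baseline. Within Group B, a patient who lost response on ixekizumab in Period 2 and was retreated leaves the denominator at every visit, back to Week 0 of the originating study. A patient who kept response stays in. That selection favours the drug.

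The same event is handled differently a few weeks later. Protocol 7.4 says "During Period 2, retreatment will begin at the next scheduled visit", and SAP 6.1.5 says "Period 3 starts at the first injection of study treatment at Week 64". A flare at Week 56, retreated at Week 60, removes the patient. A flare at Week 60, retreated with the Week 64 injection, leaves the patient in as an mNRI nonresponder.

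This population carries the other-secondary objective on long-term effect through Week 104. SAP 6.1.2.2 also states the purpose of the model-based summary: "The least-squares (LS) means will be reported to assess the maintenance of treatment effect". Response rates from a set cleared of Period 2 retreatments would be read as rates for everyone kept on ixekizumab.

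**Working it through.** **Whom the clause affects.** Placebo-arm patients are excluded in their own right, and Group A has no retreatment rule. That leaves patients re-randomised to ixekizumab and retreated in Period 2. SAP 6.1.3.1 allows retreatment for reasons other than flare, so these are almost all, but not strictly all, flares.

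**Plan inputs.** About 750 entrants; 30% in sustained remission; 2:1 re-randomisation; flare rates of 10% on ixekizumab and 70% on placebo (Protocol 5.2, 5.4 and 10.1; SAP 5.2). The plan's power claim, from which the 10% comes, reproduces: two-sided Fisher's exact test, 133 versus 67, power above 0.9999 against the stated figure of over 99%.

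**Assumed, not in the documents.** A proportion r of Group A responds (20% to 50%); remitters respond until they flare; every flare is retreated in Period 2; no attrition; the remission share is the same among patients on ixekizumab since originating Week 0.

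**Share dropped.** Per entrant who started on ixekizumab:
- Group A: 0.70. Group B kept on ixekizumab: 0.30 × 2/3 = 0.20. Protocol-defined set: 0.90.
- Retreated: 0.20 × 0.10 = 0.02. Dropped: 0.02/0.90 = 2.2%.
- In patients: 750 × 0.30 × 2/3 × 0.10 = 15. If 50-75% of entrants started on ixekizumab (assumed), 7.5 to 11.3 are affected.

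**mNRI rate after Week 64 (10% flare).**
- Retreated patients kept as nonresponders: (0.18 + 0.70r)/0.90 = 35.6% (r = 0.20) or 58.9% (r = 0.50).
- SAP population: (0.18 + 0.70r)/0.88 = 36.4% or 60.2%.
- Rise: 0.8 or 1.3 points.

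**Sensitivity to the flare rate.**

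| Ixekizumab flare rate | Dropped | Rise, r = 0.20 | Rise, r = 0.50 |
|---|---|---|---|
| 5% | 1.1% | 0.4 | 0.7 |
| 10% | 2.2% | 0.8 | 1.3 |
| 20% | 4.4% | 1.6 | 2.6 |

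**Late flares.** If flares spread evenly over the 10 Group B visits from Week 28 to Week 64 (assumed), the 2 in 10 first met at Week 60 or 64 escape the exclusion. Then 0.016/0.90 = 1.8% are dropped, the denominator is 0.884, and the rise is 0.6 to 1.1 points.

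**Cross-check by another route.** From 200 randomised: 200 × 2/3 × 0.10 = 13.3 retreated, out of 550 + 133.3 = 683.3 on ixekizumab, or 1.95%. Keeping them as nonresponders lowers a rate by that rate times 1.95%: 0.8 points at 40% and 1.6 points at 80%.

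**The case against.** The protocol does not say in words that flared patients stay in. It leaves the word consistently undefined and sends full analysis detail to the SAP. SAP 6.3.3 describes retreated patients as having stopped their originally assigned blinded treatment. A sponsor could say that the SAP only makes the protocol definition precise, with Week 64 as a natural landmark because the randomised period ends and the primary database lock falls there. This stands in part: the protocol keeps these patients by inference, and a fixed landmark is not in itself a fault. It does not explain the exclusion. The regimen is unchanged on retreatment. SAP 6.1.4 identifies patients with at least 24 months on ixekizumab as those who started on it and were not re-randomised to placebo, so there retreatment does not break continuity. The consequence that 6.1.2.2 attaches to ending assigned treatment is imputation, not removal. Parts of the SAP are redacted, so a rationale or a sensitivity analysis there cannot be ruled out.

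Flare on ixekizumab is also visible elsewhere: it is the primary endpoint in the RW ITT Population, and retreatment outcomes are tabulated for the Flare Population. That is correct and limits the harm, but it does not repair the long-term denominators.

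Four stronger readings are tempting and not supported:
- **That the exclusion turns a real loss of response since Week 24 into no loss at all.** On the inputs above the fall would be 2.2 points with the patients kept and zero without. This follows directly from assuming that remitters respond fully until flare and that Group A is constant. Remission is defined by ASDAS, and several endpoints here are ASAS or BASDAI responses.
- **That every long-term summary is inflated.** Observed-case rates could move either way if retreated patients regain response on the same drug, and no mBOCF or MMRM effect has been calculated.
- **That mNRI is confined to data after Week 64.** One sentence in 6.1.2.2 reads that way, but an earlier one covers retreatment at any time before Week 104.
- **That the primary result is affected.** It uses a different population.

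**Conclusion.** The concern holds for the mNRI summaries. SAP 6.1.1 selects on a post-baseline failure, conflicts with the SAP's own nonresponse rule, and departs from the natural reading of Protocol Table RHBY.5. On the plan's figures about 2% of the population is lost and the mNRI response rate rises by roughly 1 point: 0.8 to 1.3 at a 10% flare rate, and 0.4 to 2.6 across flare rates of 5-20%. The Group A response rate and full response among remitters until flare are assumptions. The direction for mNRI is fixed, because the patients removed would all count as nonresponders after retreatment. The tables are descriptive and outside the multiplicity scheme, so this is a modest, one-sided distortion of an other-secondary objective.

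**What to change.** - **SAP 6.1.1:** delete the Period 2 retreatment exclusion for patients re-randomised to ixekizumab. Keep the other exclusions, including patients re-randomised to placebo. State here, and in footnote a of the tables, that retreatment on the same regimen does not break the requirement of an unchanged regimen up to Week 64.
- **SAP 6.1.2.2:** state that the existing rule (mNRI for categorical, mBOCF for continuous endpoints, from the time of retreatment) applies to Period 2 retreatment, as it already reads for any time before Week 104. Make the sentence limited to data after Week 64 consistent with it. Say how retreatment for reasons other than flare is handled, since 6.3.2 names only flare. State that observed-case and MMRM summaries use only data before retreatment, as 6.1.2.2 already does for dose escalation.
- **Supportive table:** keep the present subset, labelled as conditional on no Period 2 retreatment.

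The cost is SAP wording, one extra table set and slightly lower headline mNRI rates. No new data or visits are needed.

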**Randomized Withdrawal (RW) Intent-to-Treat (ITT) Population:** Efficacy and health outcome analyses for Period 2 will be conducted on RW ITT Population, defined as all patients who achieved a state of sustained remission and were randomized to 40-week double-blind placebo-controlled RWR period (Group B), even if the patient does not receive the correct treatment or otherwise does not follow the protocol. Patients will be analyzed according to the treatment to which they are assigned.

**RW Safety Population:** Safety analyses will be conducted on the RW Safety Population, defined as all randomized patients in Group B who have received at least 1 dose of study

treatment after randomization in the specified period. Patients will be analyzed according to the treatment to which they are assigned.

**Flare Population:** Defined as all randomized patients in Group B who experience a flare after randomization at Week 24. Efficacy summaries will be conducted for Period 2 and Combined Periods 2 and 3 on the Flare Population who receive at least one injection of ixekizumab retreatment after flare in the Combined Periods 2 and 3. Patients will be analyzed according to the treatment to which they are assigned at randomization and the retreatment.

**Dose Escalation Population:** Exploratory efficacy summaries will be conducted for Period 3 on Dose Escalation Population, defined as all patients (from Group A and Group B) who have been treated ixekizumab 80 mg Q4W for at least 12 weeks, and had their dose escalated to ixekizumab 80 mg Q2W (determined by investigator).

**Follow-Up Period Population:** Safety analysis for Period 4 will be conducted on the Follow-Up Period Population, defined as all patients who have completed an originating study (RHBV, RHBW, or RHBX) through Week 52 and have entered the Post-Treatment Follow-Up Period (Period 4) in RHBY. Patients will be analyzed according to the treatment they are taking before entering Period 4.

[Table RHBY.6.1](#) displays analyses purpose and treatment groups for each analysis population and study period.

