**Table RHBY.6.1. Treatment Groups and Major Patient Populations for Analysis Periods for Study RHBY**

Population	Period	Analyses	Treatment Groups	Group Comparisons
Lead-In Period Safety Population	Combined Periods 1 & 2 Combined Periods 1, 2, & 3	Safety	IXE80Q2W IXE80Q4W Total IXE	Descriptive No inferential statistics
Long-Term Ixekizumab Treatment Efficacy Population	Combined Periods 1 & 2 Combined Periods 1, 2, & 3	Efficacy and health outcomes	IXE80Q2W a IXE80Q4W a Total IXE	Descriptive No inferential statistics
RW Safety Population	Period 2 Period 3	Safety	IXE80Q2W IXE80Q4W Total IXE Placebo	Total IXE vs. Placebo IXE80Q2W vs. Placebo IXE80Q4W vs. Placebo
RW ITT Population	Period 2 Combined Periods 2 & 3	Efficacy and health outcomes	IXE80Q2W IXE80Q4W Total IXE Placebo	Total IXE vs. Placebo IXE80Q2W vs. Placebo IXE80Q4W vs. Placebo
Ixekizumab Structure Population	At Week 56 for a 2-year assessment	Efficacy	IXE80Q2W IXE80Q4W Total IXE	Descriptive No inferential statistics
Flare Population with retreatment	Period 2, Combined Periods 2 and 3	Efficacy	PBO/IXE80Q2W PBO/IXE80Q4W PBO/IXE IXE80Q2W/IXE80Q2W IXE80Q4W/IXE80Q4W IXE/IXE	Descriptive No inferential statistics
Dose Escalation Population	Period 3	Efficacy	PBO/IXE80Q4W, IXE80Q4W/ IXE80Q4W Total	Descriptive No inferential statistics
Follow-Up Population	Period 4	Safety	IXE80Q2W IXE80Q4W Total IXE Placebo	Descriptive No inferential statistics

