#### **6.1.2.1. Lead-In Period Safety Population**

Safety data will be summarized for Combined Periods 1 and 2 and Combined Periods 1, 2, and 3 for the Lead-In Period Safety Population by Combined Ixekizumab treatment group (Total IXE) and each of the IXE80Q2W and IXE80Q4W groups without inferential statistics.

For safety analyses, unless otherwise specified, the following baselines will be used:

- For treatment-emergent adverse events (TEAEs):
  - For patients who were not randomized to placebo at Week 24 during the Combined Periods, the baseline is the events ongoing prior to the first injection in Period 1;
  - For patients who are randomized to placebo at Week 24 and then are retreated with ixekizumab, the baseline for TEAEs during Period 1 is the events ongoing just prior to the first injection in Period 1, but the baseline for TEAEs after retreatment of ixekizumab is the events ongoing just prior to the first injection of retreatment during Periods 2 and 3 Combined.
- For change from baseline to minimum/maximum postbaseline, to last observation and to each scheduled postbaseline visit for laboratory and vital signs, and for treatment-emergent abnormal laboratory and vitals, the baseline is the last nonmissing value prior to the first injection in Period 1, regardless of changes of treatment regimen after Week 24.

The categorical safety measures will be summarized with frequency counts and incidence rates.

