### ***6.1.3. General Considerations for Analyses during the Extension Period Including the Double-Blind RW Period (Period 2)***

#### **6.1.3.1. RW ITT and RW Safety Populations**

For patients who are randomized in Period 2 (group B), comparisons between Combined Ixekizumab treatment group and placebo, as well as between each ixekizumab regimen (80 mg Q2W or 80 mg Q4W) and placebo, will be performed for all analyses at each scheduled visit in Period 2 including Visit 515 at Week 64.

Period 2 starts at the first injection of study treatment after randomization (at Week 24) and ends at the following study events:

- Prior to the first injection of study treatment at Week 64 (Visit 515) for not retreated patients who have completed visit at Week 64. If injection at Week 64 is missing, the next injection date after Week 64 is used;
- Prior to the first injection of retreatment for patients who have been retreated within Period 2;
- ETV prior to Week 64.

For patients who are in the RW ITT Population and have been retreated with the ixekizumab treatment regimen due to a flare or any other reasons, only data prior to the time of the retreatment will be included in the analysis for Period 2. Data after retreatment will be imputed using nonresponder imputation (NRI) method for categorical variables and mBOCF method for continuous variables.

The observed values after retreatment will be used for other specified analysis, for example, efficacy analysis for Flare Population with Retreatment.

For efficacy and health outcomes, baseline is defined as the last available value before the first dose of study treatment in Period 2 from the originating study and, in most cases, will be the value recorded at Week 0 from the originating study.

The primary analysis method for treatment comparisons of categorical binary efficacy and health outcome variables will be a logistic regression with treatment group, geographic region, and originating study as factors using PROC Logistic with Wald method. The odds ratio and 95% CIs will be reported; treatment difference and 95% CI will also be reported. In the case when logistic regression model does not produce statistical results due to sparse data, Fisher's exact test will be used. Same analysis will also be carried out at each of other scheduled visits in Period 2.

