##### **6.1.5.2. RW Safety Population**

Unless otherwise specified, for the safety analyses during Period 3, baseline is defined as the last nonmissing assessment prior to the first injection of study treatment in Period 3 (mostly at

Week 64). For TEAEs, baseline is the events ongoing just prior to the first injection of study treatment in Period 3.

Summary statistics will be provided for AEs. No inferential statistics will be provided.

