The overall summary of AEs will also be provided for the RW Safety Population during Period 3, Long-Term Ixekizumab Treatment Efficacy Population and Ixekizumab Structure Population by treatment groups.

Follow-up emergent adverse events will be summarized for the Follow-Up Period Population for Period 4:

- FEAEE by PT.

In general, for all AE-related summaries, the number and percentage of patients experiencing the events will be presented by treatment group. In general, events will be ordered by decreasing frequency in the Combined Ixekizumab group, followed in the order of ixekizumab Q2W, ixekizumab Q4W, and placebo (when applicable) group, within SOC and/or PT for sorting.

A by-patient listing of all AEs will be provided.

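### The Period 3 adverse event summary counts events on ixekizumab retreatment as Placebo, because patients are grouped by assigned treatment and data do not stop at retreatment

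*SAP*

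**What the plan says.** SAP 6.1.1 includes in the RW Safety Population the randomized Group B patients with at least one dose of study "treatment after randomization in the specified period. Patients will be analyzed according to the treatment to which they are assigned". Table RHBY.6.1 has a single row for this population covering Periods 2 and 3. Its groups are IXE80Q2W, IXE80Q4W, Total IXE and Placebo, and its comparisons are "Total IXE vs. Placebo IXE80Q2W vs. Placebo IXE80Q4W vs. Placebo".

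For Period 2, SAP 6.1.3.1 gives retreated patients their own end of period: "Prior to the first injection of retreatment for patients who have been retreated within Period 2". For Period 3, SAP 6.1.5 has no such rule, and the period simply "ends on the date of Week 104 or the ETV before the date of Week 104". SAP 6.1.5.2 sets one baseline: "For TEAEs, baseline is the events ongoing just prior to the first injection of study treatment in Period 3". It then adds: "Summary statistics will be provided for AEs. No inferential statistics will be provided".

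SAP 6.13.2 plans the table in question: "The overall summary of AEs will also be provided for the RW Safety Population during Period 3", by treatment group.

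Under Protocol 7.3, Group B patients who flare in Period 2 or 3 go back to their Period 1 ixekizumab regimen. SAP 5.1 carries the treatment in use at the end of Period 2 into Period 3. Placebo patients retreated in Period 2 therefore begin Period 3 on ixekizumab.

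**The concern.** Followed as written, an AE that starts while a placebo-assigned patient is on ixekizumab retreatment goes into the Placebo column. The rest of the safety plan follows the drug actually taken:

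- The combined-period analyses drop data collected on placebo (SAP 6.1.1). They also re-baseline at retreatment: "the baseline for TEAEs after retreatment of ixekizumab is the events ongoing just prior to the first injection of retreatment" (SAP 6.1.2.1).
- Period 4 groups patients by the treatment they were taking before entering it.
- The Flare Population is grouped by randomized arm and retreatment together, and SAP 6.1.1 says so. The RW Safety definition does not.

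The Period 3 column could be misread as a late placebo event rate. SAP 6.13.1 plans exposure for this population in Period 2 only, so the reader could not see how much of the Placebo time was on drug.

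Mixing pulls the columns together. If the true ixekizumab-to-placebo rate ratio were 2.0 (an assumption) and 70% of Placebo time were on ixekizumab, the table would show 2.0 / (0.70 × 2.0 + 0.30) = 1.18.

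**Working it through.** The plan gives no figure for this table, so the size has to be built from its inputs. The plan's related figure does reproduce: Fisher's exact test with 133 vs 67 patients and flare rates of 10% vs 70% has power above 99.99%, against a stated figure of over 99%.

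**Inputs**
- 200 randomized 2:1, so 200/3 = 66.7 on placebo; placebo flare rate 70% (SAP 5.2). I add 50% as an assumed lower value.
- Retention of 85% at one year (SAP 5.2). Assumption: it applies to Group B in Period 2 whether or not a patient flares.
- Visits every 4 weeks in Period 2, then Weeks 76, 88, 100 and 104 (Protocol Section 2).
- Retreatment at the next scheduled visit in Period 2; at that visit or an earlier unscheduled one in Period 3 (Protocol 7.4).
- Assumptions: constant flare hazard, so the flare-free share after w weeks is S^(w/40) with S = 0.3 or 0.5; no dropout within Period 3.

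**1. Entering Period 3.** 66.7 × 0.85^(40/52) = 66.7 × 0.882 = 58.8 patients. Over 40 weeks that is 58.8 × 40/52.18 = 45.1 patient-years (PY).

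**2. Already on ixekizumab.** Flares established by Week 60 are retreated by Week 64.
- 70%: 1 − 0.3^0.9 = 0.662, so 38.9 are retreated. The other 19.9 are 2.26 with a flare at Week 64 and 17.65 flare-free.
- 50%: 1 − 0.5^0.9 = 0.464, so 27.3 are retreated. The other 31.5 are 2.11 and 29.42.

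**3. No new flares; Week 64 flares retreated at Week 76.**
- Randomized-arm reading, 70%: placebo time is (17.65 × 40 + 2.26 × 12)/52.18 = 14.0 PY, so the ixekizumab share is 1 − 14.0/45.1 = 69%. At 50%: 23.0 PY, 49%.
- Period-specific reading, 70%: the column is 19.9 × 40/52.18 = 15.3 PY, of which 2.26 × 28/52.18 = 1.2 PY (8%) is on ixekizumab. At 50%: 1.1 of 24.2 PY (5%).

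**4. Same hazard continues.** New flares first seen at Weeks 76, 88 and 100 number 5.35, 3.73 and 2.60 (70%), or 5.52, 4.49 and 3.64 (50%).
- Slow case, retreatment at the next scheduled visit, 70%: (2.26 × 28 + 5.35 × 16 + 3.73 × 4)/52.18 = 3.1 PY, 21% of 15.3; 11.3 patients switch. At 50%: 3.2 PY, 13% of 24.2; 12.1 patients.
- Fast case, unscheduled visit straight after detection, 70%: (2.26 × 40 + 5.35 × 28 + 3.73 × 16 + 2.60 × 4)/52.18 = 5.9 PY, 39%; 13.9 patients. At 50%: 6.2 PY, 26%; 15.8 patients.
- Randomized-arm reading, 70%: add 38.9 × 40/52.18 = 29.8 PY. Then (29.8 + 3.1)/45.1 = 73% and (29.8 + 5.9)/45.1 = 79%. At 50%, add 20.9 PY: 53% and 60%.

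Share of the Placebo column's patient-years on ixekizumab:

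| Reading of assigned | Flare rate | No new flares | Hazard continues |
|---|---|---|---|
| Randomized arm | 70% | 69% | 73–79% |
| Randomized arm | 50% | 49% | 53–60% |
| Start of each period | 70% | 8% | 21–39% |
| Start of each period | 50% | 5% | 13–26% |

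**Cross-check.** With no dropout and no visit lag at 70%, 66.7 × 0.70 = 46.7 patients are retreated. The share is 70% with no new flares, or 1 − 0.3 × 0.7/1.204 = 83% with a constant hazard (1.204 = −ln 0.3). Direction and scale agree.

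**The case against.** SAP 6.1.1 never says when assignment is fixed. The definition is tied to a specified period, and SAP 6.6 counts patient flow by assignment at the start of each period. On that reading most of the problem goes. This stands as a limit on size, but it does not remove the gap: patients first retreated during Period 3 still have no stop. SAP 6.6 covers disposition only, and the RW ITT definition uses the same grouping sentence, where it plainly means the randomized arm.

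Grouping by assigned arm is also a recognised choice. The protocol's population table states the same rule, and splitting at retreatment gives up the randomized groups. That is a real cost. But the SAP itself cuts Period 2 at retreatment for this population and gives no reason to treat Period 3 differently.

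Post-retreatment events are not lost. The combined-period tables count them as ixekizumab, and a by-patient AE listing is planned. That is why the point is minor.

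The fast-case bound can be challenged. If Week 64 flarers started Period 3 on ixekizumab, they would never enter the Placebo column under the period-specific reading, and 39% becomes 4.2/13.5 PY = 31% (26% becomes 4.6/22.5 = 20%). As an upper limit it remains fair: the central laboratory CRP is entered only once available after the visit (Schedule of Activities), so such a patient can take a placebo dose first.

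**Conclusion.** The concern holds. By its own rules, the Period 3 AE summary places events on ixekizumab under Placebo: for every retreated placebo patient if assigned means the randomized arm, and for those first retreated in Period 3 if it is read by period. The wording does not tell a programmer which reading applies.

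The shares rest on retention borrowed from one-year figures, an assumed constant hazard and no Period 3 dropout. They describe who is in the column; they are not bias in a planned test.

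The consequence is small. Protocol 10.3.4 bases primary safety on Period 2, and SAP 6.1.5.2 rules out inference in Period 3. The correction is worth making because it is cheap, but no main conclusion depends on it.

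**What to change.** Amend SAP 6.1.1, 6.1.5.2 and Table RHBY.6.1 for the Period 3 AE summary:

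1. End a placebo patient's Placebo time at the first retreatment injection, as in Period 2. Show later time in a PBO/IXE column, a label Table RHBY.6.1 already uses for the Flare Population, and give patient-years per column.
2. For patients first retreated during Period 3, reset the treatment-emergent baseline at retreatment, as SAP 6.1.2.1 does. Patients retreated before Week 64 keep the SAP 6.1.5.2 baseline.
3. Keep IXE80Q2W, IXE80Q4W and Total IXE for ixekizumab-assigned patients. Cut Q4W time at escalation to Q2W, as SAP 6.1.2.2 does for long-term efficacy, or footnote it.
4. Note that the continuing placebo patients are few, selected for not flaring, and not a randomized comparator.
5. Limit the comparisons with placebo in this row of Table RHBY.6.1 to Period 2, to agree with SAP 6.1.5.2.

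The same clarification should cover the Period 3 compliance summary for this population in SAP 6.8.

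The cost is SAP wording, one cut date (SAP 6.13.1 already uses the first retreatment dose date), a second baseline for patients who switch in Period 3, and an escalation cut or footnote. The price is that the Period 3 columns are no longer randomized groups and the Placebo column is small.
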